6. TREATMENTS

6.1. Treatments Administered

Study drug supplied for this study must not be used for any purpose other than the present study and must not be administered to any person not enrolled in the study. Study drug that has been dispensed to a patient and returned unused must not be re-dispensed to a different patient.

6.2. Investigational Study Drug

Detailed information describing the preparation, administration, and storage of givosiran and placebo is provided in the Pharmacy Manual.

6.2.1. Description

The givosiran drug product (ALN-AS1) will be supplied as a sterile solution in water for SC injection. See the Pharmacy Manual for further details of solution concentration and fill volume.

The control drug for this study will be a placebo (sodium chloride 0.9% w/v for SC administration). Placebo will be provided by the Sponsor; it will be packaged identically to givosiran and an identical volume will be administered.

6.2.2. Dose and Administration

The study drug should be injected into the abdomen or upper arms or thighs. Detailed instructions for study drug administration are presented in the Pharmacy Manual. As is consistent with good medical practice for subcutaneous drug administration, patients will be observed for a minimum of 20 minutes after each injection. Treatment for anaphylactic reactions should be readily available where patients are being dosed, and follow country and/or local hospital treatment guidelines (28).

Givosiran will be administered by a qualified and authorized health care professional trained in the recognition and management of anaphylactic reactions, whenever possible. Study drug administration may be conducted at a location other than the study center by a home healthcare professional, where applicable country and local regulations and infrastructure allow, after consultation with the medical monitor, during particular study visits, as specified in the Schedules of Assessments (Table 2 and Table 3). If the patient is unable to come to the study site, and a visit by a home healthcare professional is not possible due to circumstances related to the COVID-19 pandemic, givosiran may be administered by the patient or the caregiver under the oversight of the Investigator, and following consultation with the medical monitor, as allowed by applicable country and local regulations. In such cases, the patient or caregiver must receive appropriate training on givosiran administration and the use of epinephrine (epi pen or equivalent) prior to dosing. This measure is intended to remain in effect only during periods of time when the COVID-19 pandemic impedes the ability of patients to travel to the study site or healthcare professionals to go to patients' homes for dosing. However, study drug administration at the study center should be considered for patients who have ongoing study drug-related AEs or known risk factors for developing anaphylactic reactions, including but not limited to: prior history of an anaphylactic reaction to food, medications or due to unknown etiology, worsening injection site reactions with repeat dosing, or anyone in the opinion of the investigator that would benefit from clinical observation following dosing.

ALT and total bilirubin (TBL) results collected within 6 weeks of study drug administration must be reviewed prior to dosing. In the event that givosiran is administered offsite by the patient or caregiver, safety laboratory assessments other than ALT and TBL must be obtained from a central or local laboratory within 3 months prior to dosing. For patients with new signs or symptoms, appropriate evaluation, including laboratory assessments, should be performed based on investigator judgment prior to study drug administration.

If a patient does not receive a dose of study treatment within the specified dosing window, the Investigator should contact the medical monitor. After such consultation, the dose may be administered or will be considered missed and not administered.

Patients will be permitted to miss one dose of study drug during the 6-month treatment period and one dose within each 6-month interval of the OLE period. However, if a patient misses multiple doses, the Investigator, in consultation with the medical monitor, will discuss whether the patient will be able to continue receiving study drug while on the study.

Detailed instructions for study drug administration are presented in the Pharmacy Manual. In addition, instructions and procedures related to administration of givosiran by a patient or caregiver will be provided in the Patient/Caregiver Storage and Administration Instructions.

6.2.2.1. During the 6-Month Treatment Period (Day 1 to Month 6)

Patients will be administered givosiran 2.5 mg/kg or placebo as an SC injection once a month.

To maintain the blind, the syringes are to be masked prior to study drug withdrawal from the masked vial. At the Month 6 study visit, following the completion of all Month 6 assessments, including the urine sample for ALA and PBG levels (to end the double-blind period), patients will be administered their first open-label (unmasked) dose of givosiran to begin their participation in the open-label extension portion of the study.

6.2.2.2. During the Open-Label Extension Period (After Month 6 through End of Treatment)

Patients who crossed over to the OLE period prior to implementation of amendment 3 (ie, under amendment version 1 or 2) and are receiving 2.5 mg/kg once monthly will remain on that dose. Upon entry to the OLE period under amendment version 3, patients will cross over to receive a 1.25 mg/kg once monthly dose of givosiran. After implementation of amendment 3 and until implementation of amendment 5, a dose increase to 2.5 mg/kg once monthly may be permitted starting at Month 13 for patients receiving 1.25 mg/kg once monthly (see Section 6.2.3.4).

Upon implementation of amendment 5, all patients receiving 1.25 mg/kg givosiran once monthly who do not have ongoing clinically relevant transaminase elevations will have their dose increased to 2.5 mg/kg givosiran once monthly per guidance in Section 6.2.3.4.

6.2.3. Dose Modifications

During the 6-month double-blind treatment period, no study drug dose modifications will be allowed, except in response to LFT elevations as described in Section 6.2.3.1.

During the open-label extension period, dosing modifications will be allowed under the following circumstances:

- In response to LFT elevations as described in Section 6.2.3.1
- After implementation of amendment 3 and until implementation of amendment 5, patients assigned to the once monthly 1.25-mg/kg treatment group who experience inadequate disease control may be allowed to have their monthly dose increased to 2.5 mg/kg starting at Month 13 (when 6 months of open-label givosiran dosing have been completed at 1.25 mg/kg) based on discussion and agreement by the Investigator and medical monitor, demonstration of tolerability givosiran, and fulfillment of ALA and clinical activity criteria as described in Section 6.2.3.4.
- Upon implementation of amendment 5, all patients receiving 1.25 mg/kg givosiran once monthly who do not have ongoing clinically relevant transaminase elevations will have their dose increased to 2.5 mg/kg givosiran once monthly based on tolerability alone, without any criteria for ALA reduction or clinical activity. See Section 6.2.3.4 for further information on dose escalation.

If a study drug-related AE occurs in a patient that the Investigator judges as presenting a potential risk to the patient for further dosing, the study drug dose may be held at the discretion of the Investigator and the medical monitor should be contacted.

6.2.3.1. Monitoring and Dosing Rules Based on Liver Function Test Results

ALT and TBL results should be reviewed within 6 weeks prior to dosing.

For any ALT elevation $>3\times$ ULN (or $>3\times$ baseline in patients with elevated baseline) or >300 U/L (whichever is lower), results should be confirmed by the central laboratory (within 2 to 3 days, but no greater than 7 days). If such ALT elevations are confirmed, the additional hepatic assessments shown in [Table 5](#) should be obtained.

Subjects with abnormally elevated hepatic laboratory values (eg. ALT, AST, TBL, or INR) or signs/symptoms of hepatitis may meet criteria for withholding study drug. Criteria for withholding, monitoring and stopping study drug dosing are detailed in [Table 4](#):

Table 4: Monitoring and Dosing Rules in Patients with Alanine Transaminase (ALT) Elevations

ALT Transaminase Level	Patients with Normal Baseline ALT	Patients with Elevated Baseline ALT ^a
>3× to 5× ULN or Baseline	
 • Discontinue dosing when ALT is >3×ULN and patient is symptomatic^b, or has TBL ≥2×ULN or INR >1.5 (for patients not on warfarin), and there is no alternative cause • Otherwise, dosing may continue with monitoring every 2 weeks (±7 days)^c that includes LFTs per Table 7 and INR • If the ALT elevation persists for ≥2 months, discussion with the medical monitor is required before continuing dosing. 	
 • Discontinue dosing when ALT is >3× baseline or >300 U/L (whichever is lower) and patient is symptomatic^b, or has TBL >2×ULN or INR >1.5 (for patients not on warfarin), and there is no alternative cause • Otherwise, dosing may continue with monitoring every 2 weeks (±7 days)^d that includes LFTs per Table 7 and INR. • If the ALT elevation persists for ≥2 months, discussion with the medical monitor is required before continuing dosing.
>5× to 8× ULN or Baseline	
 • Discontinue dosing when ALT >5× to 8× ULN and patient is symptomatic^b, or has TBL ≥2×ULN or INR >1.5 (for patients not on warfarin) and there is no alternative cause • For patients who are asymptomatic and do not have INR >1.5 or TBL ≥2x ULN: 
 – Hold dosing if ALT >5×ULN, until ALT recovers to ≤2×ULN – Dosing can be resumed when ALT recovers to ≤2 x ULN according to Section 6.2.3.1.1, and following discussion with the medical monitor • Perform weekly (±3 days) monitoring of LFTs per Table 7 and INR until ALT declines to 	
 • Discontinue dosing when ALT >5× to 8× baseline or >300 U/L (whichever is lower) and patient is symptomatic^b, or has TBL ≥2×ULN or INR >1.5 (for patients not on warfarin) and there is no alternative cause • For patients who are asymptomatic and do not have INR >1.5 or TBL ≥2x ULN: 
 – Hold dosing if ALT >5×baseline or >300 U/L (whichever is lower), until ALT recovers to ≤2×baseline – Dosing can be resumed when ALT recovers to ≤2 x baseline according to Section 6.2.3.1.1, and following discussion with the medical monitor

ALT Transaminase Level	Patients with Normal Baseline ALT	Patients with Elevated Baseline ALT ^a
	
$\leq 3 \times \text{ULN}$; then monitor every 2 weeks (± 7 days) until ALT level reaches $2 \times \text{ULN}$^c
 
 If the ALT elevation persists for ≥ 2 months, discussion with the medical monitor is required before continuing dosing. 	
 Perform weekly (± 3 days) monitoring of LFTs per Table 7 and INR until ALT declines to $\leq 3 \times \text{baseline}$; then monitor every 2 weeks (± 7 days) until ALT level reaches $2 \times \text{baseline}$^d If the ALT elevation persists for ≥ 2 months, discussion with the medical monitor is required before continuing dosing.
$> 8 \times \text{ULN}$ or Baseline	Discontinue dosing after confirmation if ALT $> 8 \times \text{ULN}$	Discontinue dosing after confirmation if ALT $> 8 \times \text{baseline}$ or $> 500 \text{ U/L}$ (whichever is lower)

Abbreviations: ALT=alanine aminotransferase; INR=international normalized ratio; LFT=liver function test(s); TBL=total bilirubin; U/L=units per liter; ULN=upper limit of normal

Note: In addition to these criteria, other assessments or evaluations may be performed per Investigator discretion, as appropriate.

^a If multiple baseline ALT measurements are available, baseline ALT will be defined as the average of the 2 most recent ALT measurements prior to the first dose administered.

^b Symptoms may include nausea, right upper quadrant pain, jaundice, with no known alternative causes identified but possibly associated with (but not limited to) such causes as hepatobiliary tract disease, viral hepatitis, alcoholic hepatitis, or non-alcoholic steatohepatitis (NASH). A clinical picture consistent with drug-induced autoimmune hepatitis, including but not limited to the presence of rash, fever, lymphadenopathy and eosinophilia in addition to elevated transaminases may also be a cause for considering dosing discontinuation.

^c The frequency of laboratory monitoring should be decreased from every 2 weeks (± 7 days) to monthly (± 7 days or during scheduled study visits) once ALT has decreased to $\leq 2 \times \text{ULN}$.

^d The frequency of laboratory monitoring should be decreased from every 2 weeks (± 7 days) to monthly (± 7 days or during scheduled study visits) once ALT has decreased to $\leq 2 \times \text{baseline}$.

For ALT, TBL, and INR testing, local laboratory results may be used to inform dosing decisions; however, parallel samples should be collected for analysis at the central laboratory.

Table 5: Hepatic Assessments in Patients Who Experience Elevated Transaminases

Hematology	
CBC with differential	
Extended Hepatic Panel	
Herpes Simplex Virus 1 and 2 antibody IgM, IgG	Herpes Zoster Virus IgM, IgG
HIV 1 and 2 ^a	HHV-6
Cytomegalovirus antibodies, IgM, IgG	HBs Ag, HBc antibody IgM and IgG
Anti-nuclear antibodies	Epstein-Barr Virus antibodies, IgM and IgG
Anti-smooth muscle antibodies	Anti-mitochondrial antibodies
HCV antibody	HAV antibody IgM
HCV RNA PCR – qualitative and quantitative	HEV antibody IgM
CPK	
Imaging	
Abdominal ultrasound with Doppler flow (or CT or MRI) including right upper quadrant	
Focused Medical and Travel History	
Use of any potentially hepatotoxic concomitant medications, including over the counter medications and herbal remedies	Alcohol consumption
Other potentially hepatotoxic agents including any work-related exposures	Recent travels to areas where hepatitis A or E is endemic

Abbreviations: AAT=alpha-1 antitrypsin; anti-LKM=anti-liver-kidney microsomal antibodies; CBC=complete blood count; CPK=creatine phosphokinase; CT=computed tomography; HAV=hepatitis A virus; HBc=hepatitis B core; HBsAg=hepatitis B virus surface antigen; HCV=hepatitis C virus; HEV=hepatitis E virus; HHV-6=human herpesvirus 6; HIV=human immunodeficiency virus; IgG=immunoglobulin G antibody; IgM=immunoglobulin M antibody; MRI=magnetic resonance imagery; PCR=polymerase chain reaction; PT=prothrombin time; RNA=ribonucleic acid; SLA=soluble liver antigen; TSH=thyroid-stimulating hormone

Note:

- All assessments will be measured in central laboratory. The full panel of assessments should only be performed once; individual assessments may be repeated, as needed.
- Additional samples may be collected for assessment of potential alternative causes of liver injury, which may include AAT, ceruloplasmin, acetaminophen/paracetamol levels, anti-LKM antibodies, toxicology screen, ferritin, parvovirus B19, anti-SLA antibodies, gamma-globulins (including IgE and IgG levels), and transferrin saturation, as clinically indicated.

^a HIV testing will not be performed where prohibited by local regulations.

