5.2. Exclusion Criteria

Each patient must not meet any of the following exclusion criteria to be eligible for enrollment in the study:

1. Any of the following laboratory parameter assessments at Screening:
 - a. Alanine aminotransferase (ALT) $>2 \times \text{ULN}$
 - b. Total bilirubin $>1.5 \times \text{ULN}$. Patients with elevated total bilirubin that is secondary to documented Gilbert's syndrome are eligible if the total bilirubin is $<2 \times \text{ULN}$
 - c. International normalized ratio (INR) > 1.5 (patients on an anticoagulant [eg, warfarin] with an INR < 3.5 will be allowed)
2. Estimated Glomerular Filtration Rate (eGFR) $<30 \text{ mL/min/1.73 m}^2$ using the Modification of Diet in Renal Disease (MDRD) formula
3. On an active liver transplantation waiting list, or anticipated to undergo liver transplantation during the blinded study treatment period
4. History of multiple drug allergies or history of allergic reaction to an oligonucleotide or to N-acetylgalactosamine (GalNAc)
5. History of intolerance to subcutaneous injection(s)
6. Known active HIV infection; or evidence of current or chronic hepatitis C virus (HCV) or hepatitis B virus (HBV) infection
7. Currently enrolled in another investigational device or drug study, or less than 30 days or 5 half-lives (whichever is longer) since ending another investigational device or drug study(s), or receiving other investigational agent(s)
8. Females who are pregnant, breast-feeding, or planning to become pregnant during the study

9. Any condition (eg, medical concern or alcohol or substance abuse), which in the opinion of the Investigator, would make the patient unsuitable for dosing or which could interfere with the study compliance, the patient's safety and/or the patient's participation in the 6-month treatment period of the study. This includes significant active and poorly controlled (unstable) cardiovascular, neurologic, gastrointestinal, endocrine, renal or psychiatric disorders unrelated to porphyria identified by key laboratory abnormalities or medical history.
10. History of recurrent pancreatitis, or acute pancreatitis with disease activity within the past 12 months prior to Screening
11. Has a major surgery planned during the first 6 months of the study
12. History of serious infection within one month prior to Screening

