7.5.6.2. Eliciting and Recording Adverse Events

Eliciting Adverse Events

The patient should be asked about medically relevant changes in his/her health since the last visit. The patient should also be asked if he/she has been hospitalized, had any accidents, used any new medications, or changed concomitant medication routines (both prescription and OTC). In addition to patient observations, AEs will be documented from any clinically relevant laboratory findings, physical examination findings, ECG changes, or other findings that are relevant to patient safety.

Recording Adverse Events

The Investigator is responsible for recording non-serious AEs that are observed or reported by the patient after administration of the first dose of study drug regardless of their relationship to study drug through the end of study. Non-serious AEs will be followed until the end of study.

The Investigator is responsible for recording SAEs that are observed or reported by the patient after the time when the informed consent is signed regardless of their relationship to study drug through the end of study. SAEs will be followed until satisfactory resolution, until baseline level is reached, or until the SAE is considered by the Investigator to be chronic or the patient is stable, as appropriate.

All AEs must be recorded in the source records for the clinical study center and in the eCRF for the patient, whether they are considered drug-related. Each AE must be described in detail: onset time and date, description of event, severity, relationship to investigational drug, action taken, and outcome (including time and date of resolution, if applicable).

For SAEs, the event(s) must be recorded in the eCRF. If the electronic data capture (EDC) is unavailable, a back-up SAE form should be completed.

For AEs that are considered AEs of clinical interest, the Sponsor or its designee should be notified within 24 hours using a supplemental AEs of clinical interest (AECI) eCRF. Additional clinical and laboratory information may be collected based upon the severity or nature of the event; see Section 6.2.3 regarding monitoring for liver or pancreas abnormalities.

Refer to CRF completion guidelines for details on reporting events in the supplemental AECI eCRF.

Recording an ISR

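### Table 4, ALT >5× to 8× row: an asymptomatic warfarin patient with INR >1.5 and TBL <2×ULN meets neither the discontinue bullet nor the hold bullet

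*Protocol*

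**What the plan says.** Protocol Section 6.2.3.1 makes Table 4 the source of the rules: "Criteria for withholding, monitoring and stopping study drug dosing are detailed in" that table.

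In the ALT >5× to 8× row, both columns have the same structure:

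- **Discontinue bullet.** Applies when the patient is symptomatic, or "has TBL ≥2×ULN or INR >1.5 (for patients not on warfarin) and there is no alternative cause".
- **Hold bullet.** Opens "For patients who are asymptomatic and do not have INR >1.5 or TBL ≥2x ULN". The hold is nested under that opening; in the normal-baseline column it reads "Hold dosing if ALT >5×ULN, until ALT recovers to ≤2×ULN". The elevated-baseline column uses >5× baseline or >300 U/L, whichever is lower, with recovery to ≤2× baseline.
- **Further bullets, not conditional on INR or warfarin.** Weekly LFT and INR monitoring, and a medical-monitor discussion before dosing continues if the elevation lasts 2 months or more.

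The >3× to 5× row has a default: "Otherwise, dosing may continue with monitoring every 2 weeks". The >5× to 8× row has none. Above 8× (elevated baseline: or >500 U/L, if lower), dosing is discontinued after confirmation, whatever the INR.

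Exclusion criterion 1c (Section 5.2) sets an INR ceiling of 1.5 at screening, with an exception: "patients on an anticoagulant [eg, warfarin] with an INR < 3.5 will be allowed".

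**The concern.** The two bullets look designed to divide the row between stopping and holding, but they treat INR differently. The discontinue bullet disregards a raised INR in a warfarin patient, where it may only reflect the anticoagulant. The hold bullet then uses that same INR to shut the patient out of the hold. A warfarin patient at INR 1.4 must be held; the same patient at INR 2.0 has no stated action.

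What is at stake is a mandatory dose hold in a patient whose ALT is above five times the limit. The silence also reaches rechallenge. Section 6.2.3.1.1 requires permanent discontinuation if a Table 4 withholding rule is met on rechallenge at 1.25 mg/kg. A patient in this cell does not literally meet a withholding rule, so that stop is not triggered either.

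**Working it through.** No sample size, power or alpha figure is involved. The check codes the two bullets as logical rules for ALT >5× to 8× and counts the outcomes.

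**Inputs** (Table 4, >5× to 8× row; each yes/no): S = symptomatic; T = TBL ≥2×ULN; I = INR >1.5; W = on warfarin; A = alternative cause present.

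**Rules as written**

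- Discontinue = (S or T or (I and not W)) and not A
- Hold = not S and not (I or T)

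**The patient in question** (S = no, T = no, I = yes, W = yes)

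- Discontinue: S and T are no, and (I and not W) is no because W is yes. Result: no, whatever A is.
- Hold: not S is yes, but (I or T) is yes. Result: no.

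**Count with no alternative cause** (A = no; 2⁴ = 16 combinations)

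- Discontinue: S = yes gives 8; S = no with T = yes gives 4; S = no, T = no, I = yes, W = no gives 1. Total 13.
- Hold: S, T and I all no, W either way: 2.
- Neither: 16 − 13 − 2 = 1, the warfarin patient.

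**Count with alternative cause included and applied to every criterion** (2⁵ = 32)

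- A = no: 1 uncovered, as above.
- A = yes: the discontinue bullet never applies and the hold bullet covers 2 of 16, so 14 are uncovered.
- Total uncovered: 1 + 14 = 15 of 32. Two of these are the warfarin patient (A = no and A = yes).

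**If the alternative-cause phrase qualifies only the INR criterion**, 3 of 32 are uncovered. Two are again the warfarin patient; the third is an asymptomatic patient not on warfarin with INR >1.5, TBL <2×ULN and an alternative cause. The warfarin cell is open on either reading.

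**After adding the warfarin exemption to the hold bullet**, Hold = not S and not ((I and not W) or T):

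| Grid | Uncovered as written | Uncovered after the change |
|---|---|---|
| No alternative cause, 16 combinations | 1 | 0 |
| Alternative cause applied to every criterion, 32 | 15 | 13 |
| Alternative cause applied to INR only, 32 | 3 | 1 |

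The 13 that remain all involve an alternative cause: 8 − 1 = 7 not on warfarin and 8 − 2 = 6 on warfarin. The discontinue rule is unchanged, so no patient leaves it.

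**Does anything else mandate a hold?**

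- Central confirmation within 7 days and the Table 5 work-up (Section 6.2.3.1) investigate the event; they do not stop a dose.
- Weekly monitoring (Table 4) is observation.
- ALT >3×ULN is an event of clinical interest (Section 7.5.6.1), for which "the Sponsor or its designee should be notified within 24 hours" (Section 7.5.6.2). That is reporting.
- The medical-monitor discussion binds only once the elevation has lasted 2 months. With monthly dosing, a dose can fall due sooner.
- Section 6.2.3 provides that "the study drug dose may be held at the discretion of the Investigator and the medical monitor should be contacted". This is optional, and it presupposes a drug-related event that the investigator judges a risk to further dosing.

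**The case against.** The best reply is that the hold bullet is plainly meant as the complement of the one above it. Both list symptoms, INR and TBL, so INR >1.5 in the second can be read as the criterion just defined, warfarin exemption included. Any other reading protects a warfarin patient less at a higher INR, which nobody would intend. As a statement of intent this stands. As a reading of the text it needs words the bullet does not contain, in a table that writes the exemption out each time INR appears in a discontinue bullet.

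The second reply is rarity. Warfarin use, INR >1.5, no symptoms, TBL <2×ULN and ALT >5× to 8× must coincide in a trial of about 74 patients. The documents give no figure for warfarin use, and criterion 1c shows only that such patients can enrol. This stands, and it limits the severity.

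Three stronger inferences are not supported:

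- *That Table 4 lets this patient go on being dosed.* It does not. The default permitting continued dosing belongs to the >3× to 5× row; the >5× to 8× row is silent.
- *That the warfarin patient is the only gap in the row.* That holds only when an alternative cause is assumed absent.
- *That efficacy results are affected.* Nothing in the protocol or SAP points to this.

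**Conclusion.** The gap is literal and appears in both columns of the >5× to 8× row. It is an omission of wording rather than a contested design decision, and it is minor. Its size is 1 of 16 combinations when no alternative cause is present, or 2 of the 15 uncovered combinations out of 32 when alternative cause is included and applied to every criterion. These are counts of rule combinations, not of patients. The number of patients is not given and is expected to be very small.

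The conclusion rests on reading the hold bullet's INR condition as printed. It does not depend on how the alternative-cause phrase is parsed. The existing controls reduce the risk, but none of them requires the next dose to be held in this ALT range.

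**What to change.** In both columns of the >5× to 8× row, insert after INR >1.5 in the hold bullet the same parenthetical that the discontinue bullet already uses to limit that criterion to patients not on warfarin. This closes the warfarin cell and brings the patient under the rechallenge stop in Section 6.2.3.1.1. It loosens no stopping rule and needs no new assessment. The cost is an occasional extra hold in a warfarin patient, with resumption under the existing ≤2×ULN (or ≤2× baseline) rule. With alternative cause applied to every criterion, it leaves 13 of 32 combinations unaddressed, all with an alternative cause.

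A broader wording would hold every patient in the row who does not meet the discontinuation criteria. It closes those 13 as well, but at a further cost: a mandatory hold for patients with symptoms, TBL ≥2×ULN or INR >1.5 who have an alternative cause, including 7 combinations not on warfarin. That may be clinically sensible, but the sponsor should state it as a deliberate change if this wording is chosen.

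The >3× to 5× row, the other uses of warfarin in Table 4 and the eligibility criteria need no change for this point.
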